7.3 Statistical analysis

As it has been suggested as best practice for stratified randomized controlled trials, ANCOVA will be used to analyze the outcome parameters using the level of training (PGY1-3 vs PGY 4-5 and fellows) and specialities (acute care specialities vs. non-acute care specialities) as covariates.³⁵ Group assignment (unexpected death, alive) will be used as the independent variable. Demographic data will be analyzed using an unpaired Student's *t*-test or chi-square test, where appropriate.

Curved/linear regression analysis will be performed to assess the correlations between each outcome and stress as well as emotions. As it is common practice, results of Likert-like scales will be treated as interval-measures and thereby analyzed by using parametric tests.^{36,37}

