4.2 Secondary Objectives

Our secondary objectives are:

- (i) To assess if unexpected death of a simulated patient is associated with an impaired retention of technical resuscitation skills.
- (ii) To examine if unexpected death of a simulated patient is associated with future higher stress levels and stronger emotions during simulated crisis.
- (iii) To investigate the relationship between stress levels as well as emotions and future performance in crisis.

We furthermore hypothesize, that simulated death will lead to higher stress levels as well as more negative emotions and will thereby impact the ability to retain critical skills.

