6.1.4 Emotion Assessment

Emotions are inevitably linked to the occurrence of expected and unexpected death while treating a patient or patient simulator.¹⁶ As these feelings may foster or impair the learning effect, emotions that occurred throughout the simulation scenarios will be assessed. Participants will be asked to classify their emotions they experienced throughout the study by using the established Positive and Negative Affect Schedule (PANAS) at the end of each scenario. This assessment will be done immediately after debriefing of the respective scenarios.

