6.4.2 Risks

By creating a close to real setting and urging the participants to immerse into the scenario high-fidelity simulation is known to increase physiological and psychological stress throughout the simulation significantly above baseline levels. Especially with the occurrence of death, which is a potent stressor in the real clinical settings, emotions and stress might be aggravated. However, normal stress levels are reached at the end of the adjunct structured debriefings at common high stakes simulation sessions.

In order to detect any serious negative reactions to the scenarios, all scenarios will be debriefed by an experienced simulation instructor. The debriefers will specifically ask the subjects about their feelings and thoughts about the death of the “patient”, and will provide debriefing and coping strategies for dealing with death in the real life setting. Participants with overwhelming emotional responses, and who are emotionally troubled by the simulation experience, will be offered a voluntary professional referral to the counseling service of the University of Ottawa or the University of Toronto. In previous studies by one of the co-investigators ([name]) looking at highly stressful situations with over 400 front line workers and trainees, the subjects’ stress levels consistently returned to baseline levels at the end of the scenarios. Any residual negative emotions following such scenarios were consistently due to reflections on their own level of performance rather than on the emotional components of the scenarios themselves.

Furthermore there is a minimal risk of physical strain within this study. In order to minimize this risk, all participants will be familiarized with the mannequin prior to starting the first scenario.

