7. ANALYSIS

7.1 Quantitative analysis

7.1.1 Primary outcome parameter

The difference in retention of non-technical skills for crisis management between the intervention and the control group (measured by the Ottawa Global Rating), specified as the difference in performance between the initial and the retention test, will be our primary outcome.

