Five-point Likert scale

Repeated measures ANCOVA:

- Dependent variable: Score for each emotion
- Independent variable: Death vs. survival
- Covariates: Junior vs. senior; Acute vs. non-acute
- Time points: Initial and retention

For all Outcomes:

Relationships between all outcomes (determined by ANCOVA or by Pearson’s correlation) will be presented in a matrix table.

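### The planned analyses for objective (iii) do not hold initial-test performance fixed, so negative affect could appear related to later performance when it has no effect on it

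*Protocol*

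**What the plan says.** Protocol section 4.2 states objective (iii) as "To investigate the relationship between stress levels as well as emotions and future performance in crisis". The hypothesis that follows it in the same section goes further: death in the scenario is expected to raise stress and negative emotion and, through them, to affect retention.

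Two sentences describe the analysis. Protocol section 7.3 says "Curved/linear regression analysis will be performed to assess the correlations between each outcome and stress as well as emotions". The SAP, under its closing heading for all outcomes, says "Relationships between all outcomes (determined by ANCOVA or by Pearson’s correlation) will be presented in a matrix table". Neither lists model terms or says which test day supplies the stress, emotion or performance value. The only covariates named anywhere in the two documents are training level and acute versus non-acute specialty. The regression sentence and the Pearson option do not say that even these enter.

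Performance is defined in two ways. Protocol section 7.1.1 defines the primary outcome by the change, "specified as the difference in performance between the initial and the retention test, will be our primary outcome". The SAP names the OGRS total score as the dependent variable.

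On the source of emotions, protocol section 6.4.2 reports from earlier studies: "Any residual negative emotions following such scenarios were consistently due to reflections on their own level of performance". Section 6.1.4 fixes the timing of PANAS: "This assessment will be done immediately after debriefing of the respective scenarios".

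**The concern.** If doing badly at the initial test produces negative affect, and people who do badly at first also tend to score low three months later, initial performance is a common cause of both variables being correlated. Leaving it out gives an association that need not reflect any effect of emotion on retention.

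Subtracting the initial score does not solve this. A low initial score raises the change score arithmetically and through regression to the mean, so the artefact remains and its sign reverses. With the change score, negative affect would seem to help learning. With the retention score, it would seem to harm it. A curved fit has the same problem.

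What is at stake is the answer to objective (iii), and any reading of it as support for the idea that simulated death acts on retention through stress and emotion.

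**Working it through.** **The plan's own figures.** The documents give no calculation for objective (iii). The sample size in protocol section 7.2 concerns the primary comparison and reproduces: a two-sample t-test with d = 0.8, two-sided 5% and 80% power needs 26 per arm, and 52 × (1 − 0.12) = 45.76, so 46. Recruiting 56 with 20% attrition leaves 56 × 0.8 = 44.8. I use n = 45.

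**Inputs that must be assumed.** Let Y1 and Y2 be the initial and retention scores and E the post-debriefing negative affect at the initial test, all with variance 1. Let corr(Y1, E) = −a and corr(Y1, Y2) = ρ. Given Y1, E has no effect on Y2. Neither a nor ρ is in the documents. I show a = 0.1, 0.3 and 0.5 with ρ = 0.35, 0.5 and 0.7.

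**Retention score.** Cov(E, Y2) = −aρ, so the correlation is −aρ.

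**Change score, taken as Y2 − Y1.**
- Cov(E, Y2 − Y1) = −aρ + a = a(1 − ρ).
- Var(Y2 − Y1) = 2(1 − ρ).
- Correlation = a(1 − ρ)/√(2(1 − ρ)) = +a√((1 − ρ)/2).

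**Worked case, a = 0.5, ρ = 0.5.** Retention score: −0.5 × 0.5 = −0.25. Change score: 0.5 × √0.25 = +0.25.

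**Rejection rates** at nominal 5%, no true effect, n = 45, 20,000 simulated trials per row:

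| a | ρ | r with change | rejects | r with retention score | rejects | adjusted for Y1, rejects |
|---|---|---|---|---|---|---|
| 0.1 | 0.35 | +0.06 | 7% | −0.04 | 5% | 5% |
| 0.1 | 0.5 | +0.05 | 6% | −0.05 | 6% | 5% |
| 0.1 | 0.7 | +0.04 | 6% | −0.07 | 8% | 5% |
| 0.3 | 0.35 | +0.17 | 20% | −0.11 | 11% | 5% |
| 0.3 | 0.5 | +0.15 | 17% | −0.15 | 17% | 5% |
| 0.3 | 0.7 | +0.12 | 12% | −0.21 | 28% | 5% |
| 0.5 | 0.35 | +0.29 | 49% | −0.18 | 21% | 5% |
| 0.5 | 0.5 | +0.25 | 39% | −0.25 | 38% | 5% |
| 0.5 | 0.7 | +0.19 | 25% | −0.35 | 67% | 5% |

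Simulation error is below half a percentage point. With a = 0 the rate is the nominal 5%.

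**Limit of the last column.** It assumes that the observed initial score is error-free and the only confounder. With reliability 0.8 for that score (a = 0.5, ρ = 0.5, n = 46), the adjusted test rejects in 7.2% of trials, with a mean partial correlation of −0.06. Adjustment removes most of the artefact, not all of it.

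**The case against.** Several points on the other side stand.

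- **Scope.** A reader might infer that section 6.4.2 predicts the same bias for every stress measure. It does not. The sentence before the one on emotions says that "stress levels consistently returned to baseline levels at the end of the scenarios". Only residual negative emotions are tied to own performance. For cortisol, STAI and appraisal the path is plausible but the documents do not state it.
- **Directness.** Section 6.4.2 reports earlier studies, and it speaks of participants' own reflections. OGRS is scored by blinded video raters. How closely self-judgement follows the rated score, which is what a measures, is unknown.
- **Certainty.** A reader might infer that a spurious association is bound to appear. At a = 0.1 the inflation is slight, and at a = 0 there is none.
- **Commitment.** The plan does not rule out adjustment. The regression terms are unlisted and the SAP allows ANCOVA. The two strata, if entered, might absorb part of the skill difference. But the Pearson option run as written is unadjusted, and initial performance is named for neither.
- **Blanket adjustment.** Adjusting every stress measure for initial performance would be wrong. Some measures precede the scenario, so initial performance may be their consequence.

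It can also be said that the objective is secondary, that it speaks only of a relationship, and that section 8.2 calls the whole study hypothesis-generating. That limits the weight of the point but does not dispose of it: the hypothesis in section 4.2 invites a causal reading, and a hypothesis whose sign depends on the choice of performance variable is a poor guide to further work.

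**Conclusion.** The point holds for negative affect. The protocol's own account of where such emotions come from, together with the timing of PANAS, makes initial performance a likely common cause, and no planned analysis holds it fixed. For post-scenario cortisol, STAI and appraisal it is a reasonable precaution rather than a documented problem.

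The size rests on assumed correlations. Over a = 0.3 to 0.5 and ρ = 0.35 to 0.7, false-positive rates are about 12% to 49% for the change score and 11% to 67% for the retention score. At a = 0.1 they are about 5% to 8%. The opposite signs matter because the protocol and the SAP define the performance variable differently.

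A reader might take this as a criticism of the main result. It is not: arm is randomised, and the primary comparison does not depend on the association between affect and performance.

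**What to change.** Replace the unadjusted correlations for objective (iii) with regressions specified in the SAP.

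1. **Measures taken after the initial scenario** (PANAS, cortisol samples 2 to 4, post-debriefing STAI, post-scenario appraisal): regress the retention-test OGRS or checklist score on the measure, with the initial-test score on the same scale, arm and the two stratification factors as covariates. Do not correlate these measures with the change score.
2. **Measures taken before the initial scenario** (cortisol samples 0 and 1, pre-scenario STAI and appraisal): adjust for arm and the two strata only. Show the model that adds the initial score as a sensitivity analysis.
3. **Same-day correlations** may stay in the matrix, labelled as concurrent and not as evidence on later performance.
4. **Reporting:** state the test day of each variable, call the results exploratory, and note that rating error leaves some residual confounding.

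All variables are already collected, so the change is to SAP wording. The cost is up to four degrees of freedom per model: with 45 completers, 45 − 6 = 39 residual degrees of freedom against 45 − 2 = 43 for a simple correlation.

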7.2 Sample size considerations

A priori sample size calculation was performed on the basis of an estimated Cohen's *d* effect size of 0.8, which is considered large and acceptable for a teaching intervention.³³ We aim at a two-tailed level of significance of $p < 0.05$ and a power of 0.8. Using the recommended sample size estimation approach for ANCOVA³⁴ with an estimated r^2 of 0.12, derived by a previous, not now published trial ([name] et al, Learning crisis resource management: Practice versus observing, CAS 2013 Abstract 1653689, accessible at <http://www.cas.ca/English/AM-Abstracts-2013>), a number of 46 participants would be needed. In order to account for an estimated attrition rate of 20% we need to recruit 56 participants. G*Power for MAC (version 3.12, Düsseldorf, Germany) was used for sample size calculations.

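### The planned stress and emotion correlations answer secondary objective (iii) but cannot support the hypothesis that simulated death affects retention through stress or emotion

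*Protocol*

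**What the plan says.** Protocol 4.2 contains two different statements. Secondary objective (iii) is associational: "To investigate the relationship between stress levels as well as emotions and future performance in crisis". The sentence that closes the section is causal: "simulated death will lead to higher stress levels as well as more negative emotions and will thereby impact the ability to retain critical skills". The second is a mediation hypothesis, running from death to stress or emotion and from there to retention.

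The analyses that connect stress or emotion with performance are:

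- Protocol 7.3: "Curved/linear regression analysis will be performed to assess the correlations between each outcome and stress as well as emotions". No model terms are listed and no stress time point is chosen.
- SAP, For all Outcomes: "Relationships between all outcomes (determined by ANCOVA or by Pearson’s correlation) will be presented in a matrix table".

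In Protocol 7.3, arm appears in the sentence on the ANCOVA: "Group assignment (unexpected death, alive) will be used as the independent variable". In the SAP, arm enters the ANCOVAs, the repeated-measures ANCOVA of emotions and the t-tests, all of which compare the groups on one outcome at a time. The one SAP regression split by arm relates training level and specialty to cortisol, not stress to performance. Neither document plans an estimate of an indirect effect.

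**The concern.** The null of the pathway hypothesis is that the product of two effects is zero: death on stress (or emotion), and stress on retention with arm held fixed. The null of a pooled correlation is that stress and performance are unrelated across all participants. These are different hypotheses.

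The trial's own expectations separate them. Protocol 4.1 expects death to impair retention, and 4.2 expects it to raise stress. If both hold, arm is a common cause and produces a negative stress-retention correlation even when stress does nothing to retention. A reader who then cites the correlation as evidence of the pathway would be reading the arm effect twice.

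What is at stake is the mechanism message. Protocol 8.1 presents the work on stress and emotion as informing teaching beyond this particular stressor.

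**Working it through.** **1. The plan's own figure.** Inputs from Protocol 7.2: "effect size of 0.8, which is considered large and acceptable for a teaching intervention", two-sided alpha 0.05, "and a power of 0.8", and covariate adjustment "with an estimated r^2 of 0.12". An exact two-sample t-test calculation gives 26 per arm, 52 in all. Then 52 × (1 − 0.12) = 45.76, rounded up to 46, and 46 × 1.2 = 55.2, rounded up to 56. Both stated figures reproduce. The checks below use 46 analysed, 23 per arm.

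**2. Model.** Stress M = a·arm + e1, and retention Y = c·arm + b·M + e2, with var(e1) = 1 and var(e2) = 1 − b². The documents give none of a, b or c, so all are assumptions in SD units. The pathway null is a × b = 0.

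**3. Why arm alone induces a correlation.** With b = 0 and 1:1 arms, the pooled correlation is (a·c/4) / √[(1 + a²/4)(1 + c²/4)].

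- a = 0.8, c = −0.8: −0.16 / 1.16 = −0.138.
- a = 0.8, c = −0.5: −0.10 / √(1.16 × 1.0625) = −0.10 / 1.110 = −0.090.

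**4. Chance of a significant result when stress has no effect on retention (b = 0).** Simulation, 50,000 trials per row, each test at two-sided 0.05. The joint test requires a significant arm effect on stress and a significant stress slope in a model containing arm.

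| a | c | Pooled correlation | Arm effect on stress and pooled correlation | Joint test |
|---|---|---|---|---|
| 0.5 | −0.5 | 6.8% | 3.4% | 2.0% |
| 0.8 | −0.5 | 9.1% | 7.7% | 3.9% |
| 0.8 | −0.8 | 15.0% | 13.3% | 3.8% |
| 1.2 | −0.8 | 24.7% | 24.5% | 4.9% |

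Separate runs differ by about half a point; the 13.3% entry was 13.8% in a run of 20,000 trials.

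**5. The other way the pathway null can hold: death does not change stress (a = 0), but the two are related within arms.** With c = 0 and b = −0.3 or −0.5, the pooled correlation is significant in 54% or 95% of trials. Adding arm hardly changes this (53% or 95%), because the association is real. Also requiring the arm effect on stress brings it to 2.7% or 4.8%. Adding arm is therefore not sufficient; the first step must be tested too.

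**6. Is arm adjustment enough for the second step?** Protocol 6.4.2 reports that, in previous studies, leftover negative emotion came from participants' reflection on their own performance. Initial performance may therefore drive the mediator, and it plausibly predicts retention. Take a = 0.8, b = 0, c = 0, and assume initial performance correlates −0.3 with the mediator and +0.5 with retention. The joint test without initial performance is then significant in about 12% of trials; with −0.5 and +0.5, in about 29%. Adding the initial score returns it to about 4%.

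**7. Price in power.** With a = 0.8, b = −0.4 and c = 0, the joint test has about 59% to 61% power. The arm effect on stress read together with the pooled correlation has about 65% to 66%. The pooled correlation alone is significant in about 86%, but it does not test the pathway.

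**The case against.** - **The analyses fit the objective they serve.** Objective (iii) asks about a relationship, and regression or correlation answers that. A reader might infer that the plan offers the correlation as its test of the pathway. Neither document says so. This stands: the gap is that the pathway sentence has no analysis of its own, not that objective (iii) is wrongly analysed.
- **Arm may be included.** A reader might infer that arm is left out of every such analysis. That is certain only for the Pearson option. The regression sentence in 7.3 is silent on its terms, and every ANCOVA the SAP specifies carries death versus survival with both strata. This stands too, although the silence still needs filling.
- **The largest rates are not errors for objective (iii).** A reader might quote 54% to 95% as a false-positive rate. In those settings stress and performance truly are related, and the planned comparison of the arms on stress already guards the pathway reading if the two results are read together. No rule for reading them together is written.
- **The effect sizes are assumed.** True. At 0.5 SD shifts the excess is slight, and the 25% row needs a 1.2 SD stress shift that the documents do not support.
- **Everything is exploratory.** Protocol 8.2 describes all aspects of the study as hypothesis generating. That limits the consequence, but exploratory status does not make a test of one null answer another.

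**Conclusion.** The point holds in a limited form. As planned, the stress and emotion analyses can describe an association but cannot support the statement that death affects retention through stress or emotion. With shifts equal to the protocol's d of 0.8 in both variables and no stress effect, the pooled test is significant in about 15% of trials, or about 14% with a significant arm effect on stress as well, against about 4% for the arm-adjusted joint test. With shifts of 0.8 and −0.5 the first two figures are about 9% and 8%.

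These rates rest on assumed effects, normal errors, 46 completers and, for the joint test, no confounding of mediator and retention; step 6 of the working shows that the last assumption matters. The primary comparison of the arms, and the other direct comparisons between arms, are untouched. This is a low-cost improvement to an exploratory mechanism claim.

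**What to change.** In Protocol 7.3 and under For all Outcomes in the SAP:

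1. In each regression of retention performance on initial-session stress or emotion, include arm, the two stratification factors and the initial-test score of the same performance measure (OGRS for non-technical skill, the checklist score for technical skill).
2. Base any statement about the pathway on both the arm effect on the mediator and the mediator slope from that adjusted model, or on the indirect effect with a bootstrap confidence interval. Use the initial-session mediator, because section 6 switches the mannequin's outcome between the groups at the retention test. Label the result exploratory, since stress and emotion are not randomised.
3. State that the correlation matrix is descriptive.

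The cost is a few lines of text and analysis on data already being collected. Power for the mechanism claim falls when death has no direct effect, as shown in step 7 of the working. Unmeasured confounding of mediator and retention remains possible even after adjustment.

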7.4 Qualitative analysis

Qualitative data will be analyzed according to grounded theory by sorting, coding and redefining into emergent topics. Thereafter interview transcripts will be compared against each other.^{38,39} By using an iterative approach, ongoing preliminary analysis of the results gathered by the semi-structured interviews will lead to adaptation of the interviews. Thereby thematic categories will be established and continuously refined. This process will be performed until coding results in an explanation of the observations, and saturation is reached.

8. IMPLICATIONS AND LIMITATIONS

8.1 Implications

Over the past decades, high-fidelity simulation has gone from being a relatively limited teaching tool to one of the most, cutting edge ways to teach medical trainees. Several studies have demonstrated the effectiveness of simulation in teaching both technical and non-technical skills, such as Crisis Resource Management.⁴⁰⁻⁴² However, by creating an environment that requires the learners to immerse into a "make-believe world", participants are exposed to a high level of stress and

emotions.¹⁸ As of yet, no work has been done to establish precisely the impact of an unexpected simulation death on skills retention of residents.

Even though medical professionals are exposed to patient death on a regular basis, these events have been shown to be linked to a considerable emotional and stress load, even in the most experienced personnel. However, transferring such an event into the secure environment of medical simulation is a matter of current discussion.^{16,18,19} Especially, the impact of the unexpected death of a mannequin remains unclear. While some educators fear exaggerated negative feelings, distraction from the learning objective and refusal of further simulation sessions, the occurrence of death as a “to-be-remembered event”² might improve the learning outcome.⁴³ Presently, simulated death is mostly avoided partly because of lack of reliable data on its impact on learners. This study aims to compare skills retention at 3 months after experiencing or not simulated unexpected death. In doing so, we hope to provide the foundation for an evidence-based approach to effective scenario development in simulation education. The results of this trial will have immediate and practical impact on the simulation scenario design, and may serve as evidence-based guidance for the development of universal simulation guidelines.

Little is known on the emotional effects of medical education including simulation. This study is a collaborative effort between simulation experts, specialists in crisis management, stress and medical education and the findings will be applicable and generalizable across several disciplines. It is the intention of the study to evaluate a skill that is as generalizable as possible. The investigation of stress levels, cognitive load and emotions will deepen our understanding of the effects of simulation-based education on learners and will potentially help to improve teaching effectiveness. The effect of negative emotion on learning and retention has implications for education outside this particular stressor (simulated death) to other causes of learner distress and may be generalizable outside of simulation. Our insights into the effects of emotions and stress on learning and skills may be applicable to other teaching techniques, potentially having a large impact on medical education.

